6.3. Exclusion Criteria

- (1) The subject has been previously included in this study.
- (2) The subject has received, or is scheduled to receive, another investigational medicinal product (IMP) from 1 month before to 1 week after administration of fluciclovine (¹⁸F) injection.
- (3) The subject has known hypersensitivity to fluciclovine (¹⁸F) injection or any of its constituents.
- (4) The subject has had a choline PET/CT scan within 3 months of the screening visit.
- (5) The subject has bilateral hip prostheses.

7. STUDY PROCEDURES

7.1. Recruitment

The trial will be advertised in the clinical centres participating in the study using REC approved advertising materials explaining the study and providing contact information for the local study team. In addition, potential participants will be identified from their local urology MDT meeting and during outpatient oncology or urology appointments. They will be approached by a member of their clinical team within the hospital setting and be informed of the trial, or be sent information, the patient information sheet (PIS) by post. The PIS will also provide contact details for the study team should the potential participant wish to initiate contact.

If a patient expresses an interest in the study to their clinical team within the hospital setting, they will be given a PIS and will be asked to give their permission to be contacted by the study team. If this permission is given, the referring clinical team member will complete a referral form to the study team with the patient's contact details.

Upon establishing contact with the study team to indicate interest in the study, a concise explanation of the study will be provided to the patient (as detailed in section 7.2). Patients will be encouraged to raise any queries they have about the study to aid their decision regarding participation. They will be allowed as much time as wished to consider the information, and the opportunity to question the Investigator, their GP or other independent parties to decide whether they will participate in the study. This may involve more than one contact with the study team. When the patient has decided to participate in the study, an enrolment visit (Visit 1) will be arranged. Enrolment will involve checking that the patient is eligible for the study, completion of informed consent, study registration and screening. The patient's hospital notes will be made available for screening purposes. The visit is also a further opportunity to ensure all queries about the study have been addressed.

7.2. Informed Consent

The participant must personally sign and date the REC approved version of the Informed Consent form before any study specific procedures are performed. If an amendment is made to the informed consent document during the study, patients still being followed up in the study will be informed of the changes made to the document and will be asked to consent to continued participation in the trial.

Written and verbal versions of the Participant Information and Informed Consent will be presented to the participants detailing no less than: the exact nature of the study; what it will involve for the participant; the implications and constraints of the protocol; the known side effects and any risks involved in taking part. It will be clearly stated that the participant is free to withdraw from the study at any time for any reason without prejudice to future care, and with no obligation to give the reason for withdrawal.

The participant will be allowed as much time as wished to consider the information, and the opportunity to question the Investigator, their GP or other independent parties to decide whether they will participate in the study. Written Informed Consent will then be obtained by means of participant dated signature and dated signature of the person who presented and obtained the Informed Consent. The person who obtained the consent must be suitably qualified and experienced, trained in GCP and informed consent procedures, and have been authorised to do so by the Chief/Principal Investigator. A copy of the signed Informed Consent will be given to the participant. The original signed form will be retained at the study site.

7.3. Screening and Eligibility Assessment

Prior to registration or any study measures being undertaken, eligibility will be checked as detailed in section 7.1 and documented informed consent will be completed as detailed in section 7.2.

All participants will undergo clinical assessment including medical history and baseline study measures (section 7.5) over Visits 1-2 as outlined below and in Appendix A (Schedule of Study Procedures): -

7.4. Randomisation, blinding and code-breaking

All participants will receive fluciclovine (¹⁸F) injection.

7.5. Baseline Assessments

Visit 1 (after successful screening and patient informed consent obtained)

Demographics

The participant's age will be recorded.

Medical History

This forms part of the participant's routine clinical care, consisting of significant past medical history and drug history including known drug allergies.

PSA level

The dates and levels of the participant's PSA from the date of radical therapy will be recorded. These values will be obtained from the participant's hospital records. A repeat PSA level will be measured at time of screening at the same time as the clinical laboratory tests are taken.

PCa treatment history

Specific details on the treatment history for PCa will be recorded. This will include the date of initial PCa diagnosis, initial tumour stage and Gleason score, dates of radical treatment and adjuvant treatment (if given), date of BCR diagnosis. This information will be obtained from the participant's hospital records.

Imaging history

The nature, date and outcome of imaging examinations performed up to 3 months before screening will be recorded. This information will be obtained from the participant's hospital records.

Intended management plan

The management plan, based on pre-existing clinical information including results of conventional imaging, will be recorded. This information will be obtained from the participant's hospital records or MDT records.

ECG

An ECG will be performed.

Vital Signs

Sitting blood pressure and heart rate will be recorded.

Urine

Patients will be asked to provide a mid-stream specimen of urine to be tested with urine dipstick (leucocytes, nitrites, pH, protein, ketones, glucose, bilirubin, blood, urobilinogen). If the sample is positive for leucocytes or nitrites, the sample should be sent for urine microscopy and culture and if the

patient has symptoms of a urinary tract infection, this should be treated according to local guidelines prior to PET/CT. Fluciclovine (^{18}F) PET/CT can be performed during such treatment.

Clinical laboratory tests

Blood samples for clinical laboratory tests will be taken and sent for analysis at the local hospital. This will consist of haematology (red blood cell count, haemoglobin, white blood cell count with automated differential count, platelet count and haematocrit), biochemistry (electrolytes (sodium, potassium, calcium, chloride), urea, creatinine, total bilirubin alkaline phosphatase (AP), aspartate aminotransferase (AST), alanine transaminase (ALT), creatine kinase (CK), lactate dehydrogenase (LDH), albumin, total protein).

Visit 2 (day of Fluciclovine (^{18}F) PET/CT)

Vital signs

The sitting blood pressure and resting heart rate of the participant will be recorded.

Height and weight

The participant's height and weight will be measured.

Post-screening pre-administration events

A review of the participant's medical history will be performed to check for new health-related events and changes to concomitant medications since the screening visit.

7.6. Fluciclovine (^{18}F) PET/CT

The PET/CT will be acquired on the highest quality scanner available in the participating institution. The participant will be required to fast for at least 4 hours prior to the scan, drinking only sips of water within 4 hours of the scan if needed for administration of medications, and not exercise from the day before the scan through to the time of the scan. The participant will be cannulated, preferably in the right arm, and receive one dose of fluciclovine (^{18}F) diluted up to 10 mL injected by intravenous push (5-10 seconds) via the cannula with arms down followed by $\geq 10\text{mL}$ flush [54]. The participant will be scanned in the supine position in the direction of mid-thigh to skull base, with the arms positioned overhead following the dose and flush. The uptake time should be 3 to 5 minutes with a goal of 4 minutes from the end of the dose. For the PET acquisition, participants will be imaged for approximately 25 minutes. For the CT parameters, a high-quality unenhanced CT will be employed. Further details on the PET/CT acquisition will be given in the Study Imaging Manual.

Vital signs, examination of the injection site and review of AE/SAEs will be performed immediately post scan and at 60(± 5) minutes, 90(± 5) minutes and 120(± 5) minutes post-injection. All images obtained during the trial will be retained for use in this research and may be used for future approved research studies.

Analysis

Image interpretation will be based on guidelines derived from an international fluciclovine (^{18}F) reader consensus meeting held in June 2014 [54]. All readers will undergo training in interpretation of fluciclovine (^{18}F) scans, and will have a training set available for reference.

Primary evaluation and reporting of the PET/CT scan will be site-based (as per standard of care). The clinical team should make the revised treatment decision on the site-based report.

The fluciclovine (^{18}F) PET/CT scan will be centrally reported at the end of the study, blinded to the original report. Copies of the fluciclovine (^{18}F) PET/CT will be transferred from the host site for this purpose. Copies of the original report will also be transferred, as this data will be used to determine inter-reader agreement.

Prospective central review of scans will also be permitted where a second opinion is sought by a reader prior to issuing the report. This can be arranged ad hoc by contacting the co-ordinating investigator, sponsor or chief investigator.

7.7. Subsequent Visits

At each subsequent visit for the first 4 weeks following fluciclovine (^{18}F) PET/CT, study patients will be asked whether they have had any:

- Hospitalisations
- Consultations with other medical practitioners
- Disability or incapacity or other adverse event that has occurred since their last visit

24 (+ 4)-72 hours after fluciclovine (^{18}F) PET/CT (Telephone Visit 3)

A review of AE/SAEs will be performed via telephone consultation.

Outpatient appointment to review fluciclovine (^{18}F) PET/CT and revise management (Visit 4)

It is recommended that this outpatient appointment is scheduled approximately 2 weeks after the fluciclovine (^{18}F) PET/CT scan (Visit 2), although a window of 0-6 weeks is permitted depending on local clinical practice. The clinical team will then record whether the pre-scan management plan will be unchanged or altered based on the new information provided by the fluciclovine (^{18}F) PET/CT, and the reason for the decision. It is recognised that the revised management plan may be decided on before the outpatient appointment and this is permitted.

Examples of a change in proposed management plan include changing of treatment types and/or approaches (including change to radiotherapy plans), and recruitment into another clinical trial. The patient may enter another clinical trial as part of the management plan influenced by the PET/CT findings. Where an additional diagnostic procedure (e.g. imaging or biopsy) is performed in light of the PET/CT findings, the results of these should be considered prior to recording the revised management

plan, and this should be recorded on the CRF. The exception to this is where choline PET is performed in addition to fluciclovine (¹⁸F) PET/CT (see section 7.7).

The revised management plan will be discussed between the clinical team and participant, and the agreed management decision recorded. If the revised management plan and agreed management decision are different, the reason for the decision, including the influence of other standard of care assessments performed outside the trial protocol, will be documented.

The participant will also have an opportunity to report any AEs. A repeat set of clinical laboratory tests, urine dipstick analysis and ECG will also be performed during Visit 4 as part of a review for AEs.

1 month (+7 days) after fluciclovine (¹⁸F) PET/CT (Telephone Visit 5)

A review of AE/SAEs will be performed via telephone consultation.

First day of new management plan (Visit 6)

This will be performed as per standard of care and may be the same date as Visit 4, if the new management plan is commenced on the same day as the agreed treatment decision. During this visit, the investigator will record the date of management starting (to determine when follow-up information should be collected as detailed in the next heading “Clinical follow-up”).

Where patients are commencing radical salvage therapy, the investigator will also ensure that a pre-treatment PSA has been measured and recorded up to 31 days before this date.

All patients who receive radical salvage therapy

In this patient group, PSA will be measured a maximum of 31 days before therapy and at least once between 7-8 months after treatment completion. Where possible, this should be arranged to coincide with treatment-associated hospital visits as per standard of care. If these cannot be incorporated into the hospital visits, a minimum of one, maximum of two extra visits will be required for these PSA tests.

If the actual treatment received by the subject differs to the plan agreed at Visit 4, then this will be recorded on the “End of study” CRF (see the next section “Clinical follow-up”), along with the reason.

Clinical follow-up

Following instigation of their management plan, patients will be seen for follow-up at intervals as per standard of care and have imaging tests as clinically appropriate and per standard of care.

At the end of specified follow-up windows, follow-up information will be obtained by the local study team via attendance for imaging tests and via the GP or hospital medical care team as appropriate and entered on the “End of study” CRF. The patient will not be required to make a dedicated visit for this. The follow-up window is dependent on the type of management:

1. Radical salvage therapy: Up to the date of post-treatment PSA level check (7-8 months after completion of treatment).
2. Non-salvage management: Up to 6 months after Visit 6 (instigation of management plan).

In the event where radical salvage therapy is stopped prematurely or deemed by the clinical team to be sub-optimally delivered, the follow-up window should apply as for non-salvage management (up to 6 months from instigation of the initial management plan). The reasons for this should be recorded on the CRF as described in the prior section “All patients who receive radical salvage therapy”.

The following information will be collected for all patients:

1. Copies of imaging tests and reports, and histopathological reports for relevant endpoint analyses
2. PSA levels
3. Mortality (if applicable)
 - a. Date of death
 - b. Causes of death
 - c. Other significant conditions contributing to death
 - d. Source of report
 - e. Whether the death was expected
 - f. Whether a causal relationship to the study IMP is suspected
 - g. Name of the investigator responsible for assessing expectedness and causality (if the patient died prior to the last research scan or as a result of an ongoing reportable AE)

In addition, the following information on effect of management will be collected:

Radical salvage therapy	Non-salvage management
Effect of radical salvage therapy: 
 a. Treatment response 
 I. $\geq 50\%$ decline in PSA [5] \pm II. Radiological response b. Treatment failure 
 I. Increase or $< 50\%$ decline in PSA \pm II. Radiological progression 	Effect of management as assessed by the clinical team: 
 a. Response 
 I. $\geq 50\%$ decline in PSA \pm II. Radiological response b. Stable c. Progressed 
 I. PSA progression and/or II. Radiological progression d. Not assessed

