1. SYNOPSIS

Study Title	A phase 3, open-label study to assess the clinical utility of fluciclovine (¹⁸ F) PET/CT in patients with prostate cancer with biochemical recurrence (BCR) after initial treatment	
Internal ref. no. / short title	Fluciclovine (¹⁸ F) PET/CT in biochemical AL reCurrence Of prostate ca N cer (FALCON); BED-004	
Study Design	This is a phase 3, open-label study to confirm the clinical benefit of fluciclovine (¹⁸ F) PET/CT in patients with biochemical recurrence of prostate cancer (BCR).	
Study Participants	Patients with BCR being considered for radical salvage treatment (with curative intent), having had primary radical curative therapy performed at least 3 months before enrolment.	
Planned Sample Size	Recruitment of 180 patients with anticipation of 171 patients completing the trial.	
Planned Study Period	Patients will be followed up for treatment outcome and standard of care investigation results for up to 7-8 months after completion of treatment plan. Duration on study will be up to 7-8 months after completion of treatment plan.	
	Objectives	Endpoints
Primary	To assess the clinical impact of fluciclovine (¹⁸ F) PET/CT in affecting management decisions in patients with BCR being considered for radical salvage treatment (with curative intent).	The record of the revised management plan post fluciclovine (¹⁸ F) PET/CT scan in comparison to the pre-scan intended management plan.
Secondary	
 To assess possible improvement in outcome of radical salvage treatment based on fluciclovine (¹⁸F) PET/CT being included in the assessment. To assess the prostate specific antigen (PSA) threshold for positive lesion detection by fluciclovine (¹⁸F) PET/CT in BCR To assess the safety of fluciclovine (¹⁸F) injection in patients undergoing PET/CT 	
 The proportion of patients who have a sustained response to radical salvage therapy. PSA levels in relation to scan positivity will be analysed to determine the optimal PSA threshold for detecting recurrent PCa by fluciclovine (¹⁸F) PET/CT. Safety will be assessed from data on the occurrence of adverse events (AEs) and changes in clinical laboratory tests, vital signs, injection-site status, and physical examination findings from the

		time of administration of fluciclovine (¹⁸ F) injection throughout the study period.
--	--	--

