2 GENERAL PRINCIPLES

The analysis and statistical reporting will be conducted at Syne qua non using SAS version 9.2 or higher.

All listings will be based on all enrolled subjects unless specified otherwise. All tables will be presented by site and overall for the appropriate analysis population.

Descriptive summary statistics for continuous variables will include number of subjects (n), mean, standard deviation (SD), minimum, median, and maximum, unless specified otherwise. The precision of these summary statistics is defined in the table, figure and listing shells document.

Descriptive summary statistics for categorical variables will include frequency counts and percentages [n (%)]. Unless stated otherwise, the denominator for percentage calculations will be the number of subjects in the analysis set.

For treatment response baseline prostate specific antigen (PSA) is the most recent PSA measurement prior to salvage therapy for subjects who had salvage treatment and the most recent PSA measurement prior to the 18F-fluciclovine positron emission tomography/computerised tomography (PET/CT) for non-salvage subjects. If no PSA measurement is available just prior to salvage therapy, baseline will be defined as the most recent PSA measurement prior to fluciclovine (¹⁸F) scan. For all other variables, and for baseline PSA other than for treatment response, baseline is defined as the most recent value prior to fluciclovine (¹⁸F) administration.

In general, there will be no imputation of missing data, however where dates are partially missing dates may be imputed for calculation purposes, details are given under relevant section.

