5.4.2 Secondary Efficacy Analyses

5.4.2.1 Treatment response as assessed by change in PSA

An assessment of treatment response, which is based on the percentage change in PSA from baseline to the last value reported, is defined as:

- >=30% decrease in PSA will be considered to be a response to treatment
- <25% increase or <30% decrease will be classified as stable disease
- >=25% increase in PSA will be classified as disease progression

See section 2 General Principles for baseline definition.

The number, percentage and exact 95% CI of subjects having a treatment response, stable disease and disease progression, as assessed by change in PSA, will be presented overall and separately for subjects in the FAS who had salvage treatment, for subjects who had non-salvage treatment, for those with a change in management plan and for subjects with no change in management plan following the ¹⁸F-fluciclovine PET/CT scan. In addition, treatment response assessed by change in PSA will be summarised by disease location (local disease versus extra-prostatic disease) and treatment administered.

The percentage change in PSA from baseline to the last value reported will be summarised overall and by subjects who had a change in management plan versus those who did not have a change in management plan following the ¹⁸F-fluciclovine PET/CT scan, disease location and treatment administered.

Finally, a waterfall plot of the maximum percentage reduction in PSA during the 4-8 month window will be presented on the y-axis and each subject will be represented by a bar on the x-axis. The bars will be ordered in descending order of the magnitude of the percentage change in PSA value.

Treatment response and the factors used to assess the response will be listed in full.

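### The SAP's change versus no-change PSA response rates mix salvage and non-salvage patients, whose PSA runs from different baselines to different end points, so the rates are not like for like

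*Protocol*

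**What the plan says.** Protocol 7.7 (Clinical follow-up) gives two windows. For one class it is "Radical salvage therapy: Up to the date of post-treatment PSA level check (7-8 months after completion of treatment"; for the other, "Non-salvage management: Up to 6 months after Visit 6 (instigation of management plan". If salvage is stopped early or judged sub-optimally delivered, "the follow-up window should apply as for non-salvage management (up to 6 months from instigation of the initial management plan". A dated PSA is required of salvage patients only: "PSA will be measured a maximum of 31 days before therapy and at least once between 7-8 months after treatment completion". Section 7.10 defines the end of the trial for a patient along the same two lines. The synopsis gives one period for everyone: "Duration on study will be up to 7-8 months after completion of treatment plan".

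SAP section 2 also separates the starting points. For treatment response, baseline is the last PSA before salvage therapy for salvage patients, and "the most recent PSA measurement prior to the 18F-fluciclovine positron emission tomography/computerised tomography (PET/CT) for non-salvage subjects".

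SAP 5.4.2.1 then applies one rule to all: a fall of at least 30% is response, a rise of at least 25% is progression, and anything between is stable, judged on the last value reported. Rates with exact 95% intervals are shown overall, for salvage, for non-salvage, and "for those with a change in management plan and for subjects with no change in management plan". Percentage change in PSA is also summarised for change versus no change. None of the change/no-change summaries is split by management type or by length of follow-up.

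**The concern.** The secondary objective is to assess possible improvement in outcome when the scan informs treatment. A reader who sees response and progression rates side by side for patients whose plan changed and patients whose plan did not will naturally compare them. If the two groups hold different proportions of salvage and non-salvage patients, part of any difference reflects when PSA was first and last measured rather than the change of plan.

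The proportions should differ. Entrants are being considered for radical salvage (Protocol 6.2), and the only original plans listed in the SAP 5.4.1 table are salvage options and androgen deprivation. The no-change group should therefore be mainly salvage. Every move from salvage to systemic therapy or watchful waiting falls in the change group. So do patients who stay on salvage with a modified field, so the exact mix is unknown.

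The protocol kept the two classes apart: its 7.7 outcome table has separate columns with different categories. SAP 3.5, which lists departures from the protocol analysis, mentions only the loss of radiological response data.

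**Working it through.** **The plan's own figure.** The documents state no sample size or precision for PSA response. The one sizing figure is for the primary endpoint, and it reproduces: 1.96² × 0.2 × 0.8 / 0.06² = 170.7, so 171; and 171 / 0.95 = 180. It does not bear on this point.

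**1. Baseline-to-last-PSA interval from the stated rules** (T = duration of salvage treatment, not stated)

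- Salvage: the pre-therapy PSA is 0 to 31 days (1.02 months) before the start, and the last required PSA is 7-8 months after completion. Interval: 7 + T to 9.02 + T months.
- Non-salvage: screening is up to 14 days (0.46 months) before the scan (Appendix A), Visit 4 is 0-6 weeks (1.38 months) after it (7.7), the wait from Visit 4 to Visit 6 has no limit, and follow-up is then up to 6 months. Longest interval with no such wait: 6 + 0.46 + 1.38 = 7.84 months. There is no lower limit.

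The ranges overlap if T is near zero or the wait is long.

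**2. Illustrative values (assumed).** Scan-to-plan gap 1.5 months; T = 1.5 months; salvage PSA at the midpoint, 7.5 months after completion.

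- Non-salvage: 1.5 + 6 = 7.5 months.
- Salvage: 1.5 + 7.5 = 9.0 months, or about 10.0 with the full 31-day lead.

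**3. Effect on the progression class.** An uncontrolled PSA with doubling time D grows by 2^(t/D). It reaches +25% at t = D × log2(1.25) = 0.322 D. The longest doubling time scored as progression is therefore t / 0.322.

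| Interval | Months | Longest D scored as progression (months) |
|---|---|---|
| Non-salvage, 1.5-month gap | 7.5 | 23.3 |
| Salvage, T = 0 | 7.5 | 23.3 |
| Salvage, T = 1 | 8.5 | 26.4 |
| Salvage, T = 1.5 | 9.0 | 28.0 |
| Salvage, T = 2 | 9.5 | 29.5 |

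Under the step 2 assumptions, a doubling time between about 23 and 28 months is stable in one class and progression in the other. For D = 25, the rise is 2^(7.5/25) − 1 = 23% at 7.5 months and 2^(9/25) − 1 = 28% at 9 months. At T = 0 the two limits coincide.

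**4. Who can be in that band.** A post-prostatectomy patient who enters with a doubling time of 15 months or less crosses +25% by 0.322 × 15 = 4.8 months if uncontrolled, and is classed the same in either full window. The band is open to those who enter with PSA of at least 1.0 ng/mL after prostatectomy, or after radiotherapy or brachytherapy, where Protocol 6.2 sets no doubling-time limit.

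**5. Effect on the response class.** With a 1.5-month gap and a 6-month doubling time (both assumed), PSA rises by 2^(1.5/6) = 1.19 before non-salvage treatment starts. A true 30% fall from that point leaves 0.70 × 1.19 = 0.83 of baseline, scored as a 17% fall and so stable. This patient sits exactly on the cut-off, so the example shows the mechanism and not a typical size.

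Steps 3 and 5 pull differently. The earlier baseline lengthens the shorter window for untreated growth, but hides part of a fall in treated patients.

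**The case against.** The strongest reply is that little rests on these rows. The protocol's secondary endpoint concerns response to radical salvage therapy. SAP 5.4.2.1 already reports salvage and non-salvage separately, and also by treatment administered. Addendum 2 adds a salvage-only table, guided versus not guided by fluciclovine, and gives the outcome-improvement objective as its reason. No test of change against no change is planned. All of this stands. A reader might infer that the change/no-change table is the SAP's main link from scan to outcome; the documents do not support that, because the Addendum 2 table has the more direct claim and does not mix the classes.

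The second reply concerns size. A reader might count non-salvage follow-up from plan start, giving 6 / 0.322 = 18.6 months and a discordant band of 18.6-28. That ignores the pre-scan baseline in SAP section 2. With a 1.5-month gap the lower limit is 23.3, which roughly halves the band. Nor do the shorter window and earlier baseline simply compound: for untreated growth they partly offset. Treatment time is also assumed, and the salvage options include cryotherapy, HIFU and prostatectomy, for which it could be close to zero. This too stands.

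Neither reply repairs the change/no-change summaries. They remain unstratified, and rates with exact intervals shown next to each other invite the comparison whether or not a test is planned.

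On the synopsis, its wording can be read as an upper bound, so the conflict with 7.7 and 7.10 may be one of wording only.

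**Conclusion.** The concern holds as a problem of comparability in the overall row and the change/no-change summaries of SAP 5.4.2.1. The differing windows, the differing baselines and the lack of stratification are stated in the documents. The unequal mix follows from the eligibility criteria and the SAP's own plan categories. The separate salvage and non-salvage rows and the Addendum 2 table do not have this cross-class mixing.

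Size and direction cannot be derived. The documents give no treatment duration, management mix or PSA kinetics, so a percentage-point bias would be guesswork. The 23-28 month band rests on a 1.5-month gap, 1.5 months of treatment, PSA taken midway through the 7-8 month window, and growth unaffected by treatment. It shrinks to nothing as treatment time approaches zero.

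This is a worthwhile, inexpensive improvement to a secondary analysis. It does not touch the primary endpoint.

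**What to change.** In SAP 5.4.2.1:

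1. Present change versus no-change response rates, and percentage change in PSA, within management class (salvage-treated; non-salvage), using treatment received as the existing separate rows do.
2. Show separately the patients whose salvage was stopped early or sub-optimally delivered. Protocol 7.7 moves them to the 6-month window, so a salvage-only table that includes them would still mix windows.
3. Tabulate the baseline-to-last-PSA interval for each group. This is needed even within class, because non-salvage follow-up has no fixed PSA date and the SAP takes the last reported value.
4. Label the pooled overall and change/no-change rates as descriptive and not comparable.

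Keep the SAP baseline definition for the main tables. Using the last PSA before treatment for non-salvage patients should be at most a post hoc sensitivity table. The protocol requires a pre-treatment PSA only for salvage, patients on watchful waiting have no treatment start, and redefining baseline after database lock would be a data-informed change.

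Separately, the synopsis and Protocol 7.7 and 7.10 should be reconciled on study duration.

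The cost is SAP wording and a re-cut of existing data. Numbers per table are smaller and intervals wider, and the tables must be labelled post hoc if produced after lock. Addendum 2 was itself written after database lock, so there is precedent for adding tables in this way.
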